9. WEEKLY MEASURES

Weekly measures will take place at the child's home, it will last approximately 45 minutes and will take place weekly throughout the duration of 'Usual' physiotherapy and 'FES' intervention (see fig 1). In total across the whole study the CYP will receive 16 sessions of weekly measures with the SC. The weekly measures will include measures of muscle strength, walking on the level and up and down stairs on

the leg most affected by CP as well as patient reported outcomes of perceived fatigue and walking ability. We will now outline each of these in more detail.

9.1 Weekly clinical measure of impairment

9.1.1 Tibialis Anterior Strength

This will be carried out in the same way as during the baseline assessments using a handheld dynamometer, but this time it will only focus on the leg most affected by CP (see section 7.3.2 (i)) Three measures will be taken of each leg and the maximal reading used, normalised to body weight.

9.1.2 Quadriceps strength

This will be carried out in the same way as during the baseline assessments using a handheld dynamometer, but this time it will only focus on the leg most affected by CP (see section 7.3.2 (ii)) Three measures will be taken of each leg and the maximal reading used, normalised to body weight.

9.1.3 Spasticity

Spasticity in the Gastrocnemius, Hamstrings and Rectus Femoris of the most affected leg will be measured weekly using the MTS.

9.1.4 Weekly walking measure

Weekly walking assessments will be carried out in the same place each week, either at the CYP's home, local clinic or Plymouth university laboratory and this will be at the choice of the CYP and parent.

During the weekly walking assessment an electric goniometer will be placed over the knee joint (see figure 4) to measure the degree of knee flexion at initial contact and midstance in the most affected leg (for more detail see section 7.3.4). The child will then be asked to walk 5 metres on the level at a self-selected speed. During 'Usual' physiotherapy the walking assessment will be repeated three times for each condition, with the child wearing their AFO/Orthotic provision and with just their normal footwear. For the weekly walking assessment taking place during 'FES' intervention period, walking assessments will take place in the following conditions

and repeated 3 times, with FES ON and normal footwear, with FES OFF and normal footwear and with AFO/Orthotic and normal footwear. Each week the order in which the walking conditions take place will be altered.

9.1.5 Weekly Stairs measure

As above the electric goniometer will be placed over the knee joint (see figure 4) to measure the degree of knee flexion in the most affected leg as the child ascends and descends the stairs. As outlined in 7.7 of this protocol a video recording of the child ascending a descending the stairs will be taken and a tick box form will be used by the SC to describe their stair technique each week. The weekly stairs measure will be carried out with AFO's/Orthotics and their normal footwear during 'Usual' care. During FES intervention weekly stairs measures will take place with FES On/normal footwear, FES OFF/normal footwear and the CYP wearing their AFO's/Orthotics and normal footwear (See figure 5B)

9.2 Weekly Patient Reported Outcome Measures

9.2.1 Fatigue

Fatigue will be measured each week using the self-report Neuro-QOL paediatric fatigue form, which is design to measure the domain fatigue in children across a range of neurological children [23]. It consists of 11 questions regarding symptoms of fatigue experienced 'in the past 7 days', frequency of symptoms experience is then rated on a 5 point Linkert scale ranging from 'None of the time' to 'All of the time' and will take less than 5 minutes to complete [23].

9.2.2 12 Item Walking Scale

Limitations in the participants walking over the past week will be measured using a patient reported outcome measure called the 12- Item Walking Scale (Walk 12-G). It consists of 12 questions which are then rated on a Linkert scale, it is a useful measure of walking ability in people with neurological conditions [24]

9.2.3 FES activity logger

Each week during FES intervention the SC will collect data stored on the FES activity logger. This data includes the number of steps taken and the duration of use in HH:MM.

Health Research Authority

10. INTERVENTION

The intervention phase of this study is FES using either the Odstock Dropped Foot Stimulator (ODFS®) Pace or the ODFS® Pace XL device depending on CYP preference and availability. Both FES devices are a battery powered, pocket electrical device combined with a foot switch to allow precisely timed muscle stimulation while walking.

The FES devices are CE marked and approved by NICE. Both devices are described in detail (see appendix 8) using the Template For Intervention Description and Replication (TIDlieR).

Before FES intervention can begin a clinical decision will be made whether FES is going to be used to stimulate the Tibialis Anterior muscle or the Quadricep muscle in the most affected leg. This will be based on, clinical outcomes of the baseline physio assessment and will be guided by a clinical decision-making tool (see Appendix 7). FES application, training and usage is according to current paediatric UK guidance and local usual practice [25].

10.1 FES Set Up (week 9)

Once a decision is made about the muscle group being stimulated by FES the participant will be set up with an Odstock Dropped Foot Stimulator ODFS® Pace or if the participant prefers, the wireless version ODFS® Pace XL FES device. FES set will take place in week 9 with the SC at the participant preferred location (see figure 1). For Tibialis anterior stimulation, FES set up will take place with the participant in sitting. The SC will place two, 50mm x 50mm PALS Plus® square electrode pads (see figure 6A) on the lower leg, one over the head of the fibula and the other over the muscle belly of Tibialis Anterior, in accordance to the ODFS® Pace and ODFS® Pace XL manual (see figure 6B). In participants with smaller legs, the electrodes may need to be cut down to size for an accurate muscle stimulation. The SC will then turn up the FES current until a contraction is observed in the muscle and the foot begins to dorsiflex and evert.

В

Figure 6: A PALS® Plus square electrode 50mm x 50mm B FES electrode placement for Tibialis
Anterior stimulation

If the participant is being set up with FES to stimulate the quadriceps the SC will place two PALS Plus® round electrodes of either size 25mm or 32 mm (depending on the size of the child's leg) over the distal vastus medialis oblique and proximal lateralis, in accordance to the manual (see figure 7B). With the participant sat up on a bed and the knee straight, the SC will gradually increase the FES current until a contraction is observed in the quadricep muscle belly.

Figure 7: **A** PALS round electrodes

B FES electrode placement for quadricep stimulation

During FES Set Up, the participant will experience the sensation of FES activating the muscle for the first time, for some CYP this can be uncomfortable to begin with. They will be given time to get used to the sensation and can stop for comfort breaks if required. If the CYP is unable to tolerate the sensation, they can ask to stop the session and may wish to withdraw from taking part in the study. Once the FES device is set to a level that a contraction is observed in either Tibialis Anterior or the Quadricep, the SC will stick the foot switch into a cork insole, which can then be placed in the child's shoe. In most cases the foot switch will be placed in the heel of the insole (see figure 8A), but if the child is not achieving a heel strike at initial contact, the foot switch will need to be placed under the head of the first metatarsal (see figure 8B). Once the foot switch is connected to the FES device the participant is ready to trial using the FES when walking. For FES tibialis anterior set up, the FES device will be set to activate tibialis anterior when the heel or forefoot rises off the floor and through swing phase of gait. For FES quadricep set up the device will be set to activate the quadricep at initial contact and early stance phase of gait. Once the child is walking with the FES the SC may have to make further adjustments to the timing and speed of the muscle activation for optimal gait performance

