7.3.5 Walking Assessment

The walking assessment will take place across a 5-metre level walkway either in the child's home, local clinic room or University lab. The same setting will be used for each walking assessment pre and post usual physiotherapy and FES intervention. An electric goniometer will be placed over the knee joint (see figure 4) to measure the degree of knee flexion at initial contact and midstance in the most affected leg. An additional electrogoniometer will record ankle dorsi-/plantar-flexion and an accelerometer placed on the tibia to aid in the detection of initial contact while walking. Signals are sent via Bluetooth to a recording unit (Biometrics, DataLITE, UK) and analogue signal outputs are AD converted using a 1401 (CED electronics, Cambridge, UK) and recorded using Spike 2 software (version 6 CED electronics, UK).

To calibrate the electrogoniometer the output signal will be recorded while the participant is supine or sitting and the knee is passively positioned to 0 degrees and 90 degrees respectively (as confirmed using a manual goniometer). The most affected leg will be established through assessment of muscle length, spasticity and strength, taken during measures of impairment. At the pre 'Usual' physiotherapy care baseline assessment (Week 0) and the post 'Usual' physio care assessment (week 8) the CYP will be asked to complete an extensive walking assessment in the following three conditions 1.wearing their AFO's (if present) and normal footwear, 2. wearing their AFO and the FES pocket box (FES turned off and not connected to either lower limb muscle group), 3. Wearing No AFO (if safe to do so) and the FES pocket box (turned off and not connected to either lower limb muscle group), with each three conditions repeated three times (see figure 5A). In the pre 'FES' intervention and post 'FES' intervention assessment the CYP will be asked to complete the walking assessment in the following three conditions. 1. Wearing normal footwear and AFO, 2.FES ON and wearing normal footwear, 3. FES Turned off and wearing normal footwear, with each condition repeated three times. (see figure 5B).

Figure 4. Electric goniometer placement for walking and stairs assessment

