10.2 Intervention Training

The CYP and their parent will receive training on using their FES device. General training will include donning and doffing of the FES device, use of the FES, care of the electrode, electrode placement and potential adverse skin reactions to electrode pads. All of this will be documented in an information leaflet (see Appendix 4) for them to take home with their FES device. Participants will be taught how to monitor possible training effects of FES such as; transient muscle fatigue, and post exercise muscle soreness, which are normal physiological responses to walking practise whilst wearing FES.

[figure not shown]

Figure 8. A Placement of foot switch in the heel of cork insole. B Placement of the foot switch on the 1st metatarsal head

Once FES training is complete the CYP will be issued with the FES devices and bag of accessories to take home.

- FES device and battery
- FES set of electrode wires and foot switch wire
- 1 Set of Electrodes
- · Airtight bag to store electrodes.
- User Instruction Manual
- Cork Insole and foot switch
- FES pouch, to hold FES device when wearing it.
- FES supporting leaflets.

Health Research Authority

Following FES training the CYP will be asked to use the FES daily, this should start in and around the house, but building up confidence to wearing it in the community setting or at school. The aim is to build up over 1 week to wearing the FES for between 2-4hours a day in preparation for starting the FES intervention phase of the study at week 11. One week after receiving FES training (Week 10), the participant will receive a home visit from the physiotherapist to check the CYP has been using it correctly and to make any changes required to optimise gait.

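### The foot-switch insole enters at week 9 but its status is not fixed for any walking condition, so either the therapeutic or the orthotic knee-angle contrast includes a footwear change of unknown size and direction

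*Protocol*

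**What the plan says.** - **Introduction of the insole.** Section 10.1 places set-up after Phase A: "FES set will take place in week 9 with the SC at the participant preferred location". At that session "the SC will stick the foot switch into a cork insole, which can then be placed in the child's shoe". Section 10.2 lists "Cork Insole and foot switch" in the take-home kit. Section 10 describes the stimulator as a "pocket electrical device combined with a foot switch to allow precisely timed muscle stimulation while walking", so FES ON cannot be walked without the switch.
- **Weekly walks (9.1.4).** In Phase A they are done "with the child wearing their AFO/Orthotic provision and with just their normal footwear". In Phase B they are done "with FES ON and normal footwear, with FES OFF and normal footwear and with AFO/Orthotic and normal footwear".
- **Hardware control (7.3.5).** At weeks 0 and 8 one condition is "Wearing No AFO (if safe to do so) and the FES pocket box", with the box off and unconnected. The insole and switch are not mentioned. The weekly Phase A walks, which supply the serial data, do not include the box either.
- **Objectives (13.2).** The primary objective is the therapeutic effect on knee flexion at initial contact and midstance. The immediate orthotic effect is a secondary objective.
- **Analysis (15.1).** Phase A and Phase B serial points are compared, without saying which Phase B condition is set against which Phase A condition.

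The protocol does not say which shoe takes the insole, how thick it is, or whether it is removed for FES OFF or AFO walks.

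**The concern.** One label, normal footwear, covers two physical states: the child's own shoe in Phase A, and in Phase B a shoe that for some or all walks contains a cork insole and switch. The insole arrives at the phase change. In an AB design with no reversal and no concurrent control, a step that coincides with the phase change cannot be told apart from a step caused by the intervention. The outcome is a joint angle at foot contact and midstance, which what lies under the foot could plausibly alter. The protocol recognises that hardware may matter, since it tests walking with the box switched off, but it leaves out the component that touches the foot. No later analysis can recover this if insole status is neither fixed nor recorded.

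**Working it through.** The protocol gives no figure to reproduce here, so the check is mainly a side-by-side reading, followed by two illustrations.

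**1. Which contrasts include a footwear change**

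| Contrast | Insole left in for FES OFF | Insole taken out for FES OFF |
|---|---|---|
| Phase A normal footwear vs Phase B FES OFF (therapeutic) | differs | same |
| Phase B FES ON vs FES OFF (orthotic) | same | differs |
| Phase A normal footwear vs Phase B FES ON | differs | differs |
| FES OFF, week 10 vs week 19 | same | same, if out at both |

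Neither reading clears all of the first three rows. If practice varies by child or week, the variation adds noise as well.

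**2. Possible size and direction in degrees (illustration)**

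Assumptions, none from the protocol: insole 2-5 mm, thigh and shank a = 0.35 m each, and all added height absorbed by knee flexion on the raised leg.

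- Leg length L = 2a·cos(θ/2), so |dL/dθ| = a·sin(θ/2).
- At θ = 30°: 0.35 × sin 15° = 0.0906 m/rad = 1.58 mm per degree. Then 2/1.58 = 1.3° and 5/1.58 = 3.2°.
- At θ = 20°: 0.35 × sin 10° = 0.0608 m/rad = 1.06 mm per degree. Then 2/1.06 = 1.9° and 5/1.06 = 4.7°.
- Varying a over 0.30-0.40 m and θ over 20-40° widens the range to about 0.8-5.5°.

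In this model flexion increases, which would hide an FES benefit. Adjustment at the hip, ankle, pelvis or other leg would shrink the change. A heel-only effect, or an insole in the other shoe, could act differently.

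**3. What a step would do to the rules in 15.1 (illustration)**

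For each shift, 100,000 series were simulated: 8 + 8 independent normal points, no trend, no FES effect, and a constant Phase B shift towards less flexion in baseline SDs. Less flexion was scored as improvement. The 2SD rule required two consecutive points beyond the same band.

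| Shift (SD) | PND > 70% | 2SD rule met | ECL > 50% |
|---|---|---|---|
| 0 | 0.3% | 7% | 46% |
| 0.5 | 2.6% | 12% | 59% |
| 1 | 11% | 27% | 70% |
| 2 | 57% | 73% | 87% |

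By symmetry, an equal shift towards more flexion meets the 2SD rule equally often, but on the side of worsening, and makes the other two rules less likely to show improvement. The protocol gives no SD, so the degrees in step 2 cannot be converted into the shifts in step 3.

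**The case against.** The strongest reply has five parts.

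- **Insole status during FES OFF is an inference.** The insole is removable. Weeks 10 and 19 describe FES merely as turned off, without the unconnected wording used at weeks 0 and 8, which suggests the kit stays on but does not establish it. This stands. It moves the problem from one contrast to another and does not remove it.
- **The pairing of conditions is not stated.** Section 15.1 does not name it, and an analysis plan may. This also stands, but no choice of pairing can repair unmatched test conditions.
- **Unaffected data exist.** FES OFF at week 10 against week 19 is free of the step if the insole is in at both, and week 8 against week 10 would show a step at fitting, mixed with a week of build-up use. This is right and limits the damage. However, these are four in-depth assessments, summarised descriptively, and the serial weekly data carry the decision rules.
- **The insole is part of the intervention.** Appendix 8 lists it among the materials, so for FES ON a whole-system effect may be what is wanted. That is fair for FES ON, but less so for a therapeutic effect read from FES OFF walks.
- **The shoe is not specified.** That it is the study-leg shoe is inferred from the switch timing in 10.1, which follows the gait phases of the stimulated leg.

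A reader might infer that the insole effect is counted as an FES benefit in the primary outcome, in every Phase B normal-footwear walk. The documents do not support that: they fix neither insole status, pairing, size nor sign, and the simple leg-length model points towards masking.

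**Conclusion.** The concern holds in a limited form. The protocol does not standardise the insole and foot switch across conditions sharing the normal-footwear label, so the therapeutic or the orthotic contrast, depending on an unstated practice, includes a footwear change. Phase A against FES ON includes it in any case. This rests on the text alone. The size is not known: 1.3-4.7 degrees is an upper bound on assumed thickness, segment length and full compensation at the knee, and the direction cannot be determined. This is an avoidable ambiguity in test conditions, not a demonstrated bias in favour of FES. It is worth correcting because the study is meant to inform a randomised trial, where either a masked or a spurious effect would mislead.

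**What to change.** In sections 7.3.5, 7.3.6, 9.1.4 and 9.1.5:

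- State for each walking and stairs condition whether the insole is in, in which shoe, and its thickness, and record this at each session.
- For Phase A test walks in normal footwear without the AFO, and stairs where done that way, use the same type of insole in the study-leg shoe, with the switch unconnected, or a plain insole of equal thickness.
- In Phase B, leave the insole in for both FES OFF and FES ON.
- Keep the AFO condition the same in both phases.

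The cost is about one insole per child (12 in all), available from week 0 instead of week 9, and a sentence in each section. No FES unit, staff time or extra walk is needed, and stimulation and its schedule are untouched. The downside is that Phase A test walks no longer show the child's unmodified shoe. The change also does not make the phases identical: children will be more used to the insole in Phase B, and wearing the box and leads at weekly walks may still differ.

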10.2 Intervention Training

The CYP and their parent will receive training on using their FES device. General training will include donning and doffing of the FES device, use of the FES, care of the electrode, electrode placement and potential adverse skin reactions to electrode pads. All of this will be documented in an information leaflet (see Appendix 4) for them to take home with their FES device. Participants will be taught how to monitor possible training effects of FES such as; transient muscle fatigue, and post exercise muscle soreness, which are normal physiological responses to walking practise whilst wearing FES.

[figure not shown]

Figure 8. A Placement of foot switch in the heel of cork insole. B Placement of the foot switch on the 1st metatarsal head

Once FES training is complete the CYP will be issued with the FES devices and bag of accessories to take home.

- FES device and battery
- FES set of electrode wires and foot switch wire
- 1 Set of Electrodes
- · Airtight bag to store electrodes.
- User Instruction Manual
- Cork Insole and foot switch
- FES pouch, to hold FES device when wearing it.
- FES supporting leaflets.

Health Research Authority

Following FES training the CYP will be asked to use the FES daily, this should start in and around the house, but building up confidence to wearing it in the community setting or at school. The aim is to build up over 1 week to wearing the FES for between 2-4hours a day in preparation for starting the FES intervention phase of the study at week 11. One week after receiving FES training (Week 10), the participant will receive a home visit from the physiotherapist to check the CYP has been using it correctly and to make any changes required to optimise gait.

10.3 SC Training

The SC is trained Children's Physiotherapist with over 8 years of experience working with children with CP. She completed the OML® FES training course for the lower limb in 2019 and uses FES regularly for the treatment of drop foot in CYP with CP at Torbay Hospital CDC.

10.4 FES intervention

FES Intervention will begin in week 10, once the pre-FES assessment has taken place and the FES desensitisation period is complete (see figure 1). FES intervention will end in week 18.

Each CYP will be asked to use the FES device for between 2-4 hours a day, 6 days a week, for 8 weeks. This duration has been guided by PPI feedback on the study protocol and a RCT on the use of FES in drop foot in children with CP [26]. The FES can be worn at home and or at school depending on the preferences of the CYP. The CYP will be asked to avoid starting any new physical activities or sports during the period of FES intervention but may continue with their usual physiotherapy routine.

10.4 Pre and Post FES assessment

Before FES intervention can begin the participant will need to complete their pre-FES physio assessment (week 10) (see figure 1). This will last approximately 90 minutes and will take place at the participants' home, local clinic or University laboratory, depending on parent and child preference with the SC. The pre-FES

assessment will consist of the clinical measures of impairment, GOAL questionnaire and kinematic measures of walking outlined in 7.3 of this protocol.

Once FES intervention is complete the CYP will receive a post FES assessment (week 19) with the SC (see figure 1). This will consist of the clinical measures of impairment, GOAL questionnaire and kinematic measures of walking outlined in 7.3. Once the post FES assessment is complete the CYP will need to return the FES device to the study co-ordinator.

